### **9.2.2 Reporting Procedures for Serious Adverse Events**

The investigator is responsible for ensuring that all serious adverse events observed by the investigator or reported by the subject that occur after signing of the informed consent through 30 days after the last day of the dosing interval of investigational product(s) are recorded in the subject’s medical record and are submitted to Amgen. All serious adverse events must be submitted to Amgen within 24 hours following the investigator’s knowledge of the event via the applicable eCRF.

After the protocol-required reporting period defined above, the investigator does not need to actively monitor subjects for serious adverse events. However, if the investigator becomes aware of a serious adverse event after this protocol-required reporting period, the investigator will report the event to Amgen within 24 hours following the investigator’s knowledge of the event. Serious adverse events reported outside of the protocol-required reporting period will be captured within the safety database as clinical trial cases for the purposes of expedited reporting.

If the electronic data capture (EDC) system is unavailable to the site staff to report the serious adverse event, the information is to be reported to Amgen via an eSAE Contingency Report Form within 24 hours of the investigator's knowledge of the event. See [Appendix B](#) for a sample of the Serious Adverse Event Worksheet/eSAE Contingency Report Form. For EDC studies where the first notification of a Serious Adverse Event is reported to Amgen via the eSAE Contingency Report Form, the data must be entered into the EDC system when the system is again available.

The investigator must assess whether the serious adverse event is possibly related to any study-mandated activity or procedure. This relationship is indicated by a "yes" or "no" response to the question: "Is there a reasonable possibility that the event may have been caused by a study activity/procedure?"

The investigator is expected to follow reported serious adverse events until stabilization or reversibility.

New information relating to a previously reported serious adverse event must be submitted to Amgen. All new information for serious adverse events must be sent to Amgen within 24 hours following knowledge of the new information. The investigator may be asked to provide additional follow-up information, which may include a discharge summary or extracts from the medical record. Information provided about the serious adverse event must be consistent with that recorded on the applicable eCRF (eg, Adverse Event Summary CRF).

If a subject is permanently withdrawn from protocol-required therapies because of a serious adverse event, this information must be submitted to Amgen.

To comply with worldwide reporting regulations for serious adverse events, the treatment assignment of subjects who develop serious, unexpected, and related adverse events may be unblinded by Amgen before submission to regulatory authorities. Investigators will receive notification of related serious adverse event reports sent to regulatory authorities in accordance with local requirements.

Amgen will report serious adverse events and/or suspected unexpected serious adverse reactions as required to regulatory authorities, investigators/institutions, and IRBs/IECs in compliance with all reporting requirements according to local regulations and GCP.

The investigator is to notify the appropriate IRB/IEC of serious adverse events occurring at the site and other adverse event reports received from Amgen, in accordance with local procedures and statutes.

### 9.3 Pregnancy and Lactation Reporting

If a pregnancy occurs in a female subject, or female partner of a male subject, while the subject is taking protocol-required therapies report the pregnancy to Amgen as specified below.

In addition to reporting any pregnancies occurring during the study, investigators should monitor for pregnancies that occur through 4 weeks after the last dose of etanercept.

The pregnancy should be reported to Amgen's global Pregnancy Surveillance Program within 24 hours of the investigator's knowledge of the event of a pregnancy. Report a pregnancy on the Pregnancy Notification Worksheet ([Appendix C](#)). The Pregnancy Surveillance Program will seek to follow the pregnant woman throughout her pregnancy and her baby up to 12 months after birth.

If a lactation case occurs while the female subject is taking protocol-required therapies report the lactation case to Amgen as specified below.

In addition to reporting a lactation case during the study, investigators should monitor for lactation cases that occur through 4 weeks after the last dose of etanercept.

Any lactation case should be reported to Amgen's global Lactation Surveillance Program within 24 hours of the investigator's knowledge of event. Report a lactation case on the Lactation Notification Worksheet ([Appendix C](#)).

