##### *Excluded Medications*

207. prior or current use of cyclophosphamide, chlorambucil, nitrogen mustard, or any other alkylating agent.

208. subject has used any of the following  $\leq$  3 months prior to screening:
- abatacept
  - anakinra
  - azathioprine
  - cyclosporine
  - gold
  - mycophenolate mofetil
  - ProSORBA column
  - Systemic tacrolimus
  - Otezla (apremilast)
209. subject has used leflunomide  $\leq$  12 weeks prior to screening
210. subject has used any of the following  $\leq$  4 weeks prior to screening:
- sulfasalazine
  - intraarticular, intramuscular or intravenous corticosteroids, including adrenocorticotrophic hormone
  - intraarticular hyaluronic acid injections
  - live vaccines
211. for subjects not on continuous analgesics, subject has taken the following within 12 hours prior to screening: acetaminophen, NSAID, hydrocodone, codeine, tramadol, propoxyphene and/or oxycodone (unless in the form of oxycontin). For subjects not on continuous analgesics, subject has taken oxycontin within 24 hours prior to screening.

*Laboratory Abnormalities*

212. Subject has laboratory abnormalities during screening, including the following:
- Aspartate aminotransferase (AST) and/or alanine aminotransferase (ALT)  $>$  1.5 x the upper limit of normal (ULN)
  - Platelet count  $<$  125,000/mm^3
  - White blood cell count  $<$  3,000 cells/mm^3
  - Absolute neutrophil count  $<$  1500/mm^3
  - Estimated creatinine clearance  $<$  50 mL/min (Cockcroft-Gault formula, calculated value to be provided to sites)
213. Subject has any other laboratory abnormality, which, in the opinion of the investigator poses a safety risk, will prevent the subject from completing the study, or will interfere with the interpretation of the study results.

*Other*

214. Female subject is not willing to use highly-effective methods of birth control during treatment and for 6 months after the end of treatment (except if at least 2 years postmenopausal or surgically sterile [hysterectomy, bilateral oophorectomy, or bilateral salpingectomy] or has had a bilateral tubal ligation).
215. Male subject with a partner of child-bearing potential is not willing to use a condom during treatment and for 6 months after the end of treatment (except for men who are surgically sterile).

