216. Male subject with a pregnant partner, who is not willing to use a condom to prevent exposure of the fetus to semen during treatment and for 6 months after the end of treatment.
217. Subject is pregnant or breastfeeding, or planning to become pregnant or breastfeed while enrolled in the study, up to the subject's last visit and for 6 months after the end of treatment.
218. Malignancy, except adequately treated non-melanoma skin cancers, cervical or breast ductal carcinoma in situ with no evidence of disease within the last 5 years.
219. Subject has known sensitivity to any of the products or components to be administered during dosing.
220. Subject likely to not be available to complete all protocol-required study visits or procedures, and/or to comply with all required study procedures (eg, PROs) to the best of the subject and investigator's knowledge.
221. History or evidence of any other clinically significant disorder, condition or disease (with the exception of those outlined above) that, in the opinion of the investigator or Amgen physician, if consulted, would pose a risk to subject safety or interfere with the study evaluation, procedures or completion.
222. Currently receiving treatment in another investigational device or drug study, or participated in any study involving administration of an investigational drug or device within 30 days or 5 terminal elimination half-lives, whichever is longer, before enrollment.
223. Other investigational procedures while participating in this study are excluded.

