## 6.9 Contraceptive Requirements

### Female Subjects

Female subjects of child-bearing potential must agree to practice true sexual abstinence (refrain from heterosexual intercourse) or use a highly effective method of contraception during treatment and for an additional 6 months after the last dose of protocol required therapies.

Contraceptive methods that achieve a failure rate less of less than 1% per year when used consistently and correctly are considered highly effective and may include: hormonal (combined estrogen and progestogen or progestogen only), contraception associated with inhibition of ovulation (oral, injectable, implantable, intravaginal, or transdermal route), intrauterine device, intrauterine hormonal-releasing system, bilateral tubal occlusion, vasectomized partner (provided that partner is the sole sexual partner of the female participant and the vasectomized partner has received medical assessment of the surgical success), true sexual abstinence when this is in line with the preferred and usual lifestyle of the subject. The reliability of sexual abstinence must be evaluated by the investigator and be the preferred and usual lifestyle of the subject.

If a female subject is suspected of being pregnant, the protocol-required therapies must be stopped immediately and may not be resumed until absence of pregnancy has been medically confirmed.

Females not of child-bearing potential are defined as: any female who has had a hysterectomy, OR bilateral salpingectomy, OR bilateral oophorectomy, OR are postmenopausal. Postmenopausal women are those who have had no spontaneous menses for at least 2 years.

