### Male Subjects

Male subjects who have had a vasectomy and received medical assessment of surgical success or whose female partner has had a bilateral tubal occlusion are not required to use additional forms of contraception.

Otherwise, male subjects with a partner of child-bearing potential must agree to practice true sexual abstinence (refrain from heterosexual intercourse) or use a condom with spermicide (if spermicide is commercially available) during treatment and for an additional 6 months after the last dose of protocol required therapies. The reliability of sexual abstinence must be evaluated by the investigator and be the preferred and usual lifestyle of the subject.

The female partner should also consider using an acceptable method of effective contraction such as: hormonal, intrauterine device, intrauterine hormonal-releasing system, female barrier method (diaphragm, cervical cap, contraceptive sponge; a female condom is not an option because there is a risk of tearing when both partners use a condom).

Male subjects with a pregnant partner must practice sexual abstinence or wear a condom to prevent exposure of the unborn child to methotrexate through semen.

Unacceptable methods of birth control for male and female subjects include birth control methods that are considered unacceptable in clinical trials and include: periodic abstinence (calendar, symptothermal, postovulation methods), withdrawal (coitus interruptus), spermicides only, and lactational amenorrhoea method.

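### Required pregnancy and lactation reporting stops about one month after treatment and is tied to etanercept alone, while the protocol asks subjects to avoid pregnancy for 6 months after all protocol therapies

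*Protocol*

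**What the plan says.** **Reporting.** Protocol Section 9.3 has two layers. For a pregnancy in a female subject or a male subject's female partner, the first instruction applies "while the subject is taking protocol-required therapies report the pregnancy to Amgen as specified below". The second is introduced as an addition to reporting pregnancies that occur during the study: "investigators should monitor for pregnancies that occur through 4 weeks after the last dose of etanercept". Two parallel sentences give lactation cases the same structure and the same 4-week, etanercept-only limit.

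**Avoidance.** Section 6.9 requires female subjects of child-bearing potential to use contraception "during treatment and for an additional 6 months after the last dose of protocol required therapies". It sets the same period for male subjects with a partner of child-bearing potential. For men whose partner is already pregnant, it requires abstinence or a condom "to prevent exposure of the unborn child to methotrexate through semen". The exclusion criteria (Section 4.1.2) agree on length. Criterion 214 excludes a woman unwilling to use contraception "and for 6 months after the end of treatment"; 215 and 216 do the same for men and condoms. Criterion 217 excludes women who are pregnant or breastfeeding, or plan to be, while enrolled, "up to the subject's last visit and for 6 months after the end of treatment".

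**Contact after treatment.** The last scheduled urine pregnancy test in Table 1 is at week 48 or early termination. The last planned contact (Section 7.2.7) is a phone call about 30 days, plus up to 7, after the last dose of the investigational products. Its stated purpose is to collect serious adverse events. Section 9.2.2 says what happens to serious adverse events learned of after the reporting period; Section 9.3 has no such sentence for pregnancies.

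**The concern.** The two sets of provisions concern the same hazard but differ in length (4 weeks against 6 months) and in starting point (last etanercept dose against last dose of any protocol therapy, or end of treatment).

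The starting point matters because methotrexate is also investigational product (Section 6.1), is assigned in two of three arms and is part of rescue. It is also the drug that Section 6.9 names when it speaks of exposure of an unborn child. Yet no post-treatment pregnancy window is tied to it by name. A methotrexate-monotherapy subject who is not rescued takes only placebo for etanercept. Read literally, the 4-week clause gives that subject no starting date; otherwise the clock runs from a placebo dose. Blinded sites cannot tell which subjects these are.

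At stake is the completeness of safety information. The safety objective covers both drugs, but required, active collection of pregnancies stops well before the end of the period in which subjects are asked to avoid them.

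**Working it through.** The plan states no figure to reproduce. The check compares the windows.

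**Inputs**
- Post-treatment monitoring: 4 weeks = 28 days (Section 9.3).
- Final phone call: day 30, or day 37 with its window (Section 7.2.7).
- Avoidance period: 6 months (Section 6.9; exclusions 214 to 217), taken as 182 days and varied from 180 to 184.

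**Step 1: what counts as during the study.** The glossary ends the study for an individual subject on the last day that protocol procedures are conducted. Section 3.5.1 includes the follow-up call in a subject's participation. The generous reading therefore extends during-study reporting to the call, which is counted from the last dose of the investigational products, methotrexate included. One limit applies: SAP Section 6.3 dates end of study at the early termination visit for subjects who withdraw prematurely, so the generous reading is safest for completers.

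**Step 2: share of the 6 months without required collection.** Share outside = 1 − (days covered / days in the period).

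| Reading | Calculation | Outside | Range for 180 to 184 days |
|---|---|---|---|
| 4-week clause alone | 1 − 28/182 | 84.6% | 84.4% to 84.8% |
| To the call, day 30 | 1 − 30/182 | 83.5% | 83.3% to 83.7% |
| To the call, day 37 | 1 − 37/182 | 79.7% | 79.4% to 79.9% |

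In days, 154, 152 and 145 of 182 are uncovered. The first row assumes that the last etanercept (or placebo) dose and the last methotrexate dose coincide.

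**Step 3: can a share of time be read as a share of pregnancies?** Only under an assumption, because the documents give no timing of pregnancies. With a constant rate, the shares are those in Step 2. With a rate that halves every h days, put λ = ln 2 / h; the share outside the first c days is 1 − (1 − e^(−λc)) / (1 − e^(−182λ)).

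| h (days, assumed) | Outside 28 days | Outside 37 days |
|---|---|---|
| 90 | 74% | 67% |
| 60 | 69% | 60% |
| 30 | 52% | 42% |
| 28 | 49% | 39% |

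For h = 60 and c = 28: 1 − (1 − 0.724)/(1 − 0.122) = 1 − 0.276/0.878 = 0.69. A statement about most pregnancies thus depends on the assumed decline; a statement about time does not.

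**Step 4: who is assigned methotrexate.** Two arms of about 280 give 2 × 280 = 560 of 840, plus rescued etanercept-monotherapy subjects. This is the number assigned the drug, not the number who could become pregnant or father a child, since it includes postmenopausal and surgically sterile subjects.

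**The case against.** The strongest reply is that a contraception period and a surveillance window serve different purposes and may differ without contradiction. A precautionary period can reasonably be longer than active follow-up. That stands in principle, but the protocol gives no reason for the difference, and none for starting the clock at etanercept alone.

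Other parts of the reply also stand:
- **Backstops.** Section 9.3's 24-hour clock runs from the investigator's knowledge, so a late pregnancy that a site hears of could still be reported. A congenital anomaly is a serious adverse event, and Section 9.2.2 captures those learned of late. Late pregnancies are not barred from collection; they are just not actively sought.
- **Anchors usually coincide.** Both products are scheduled weekly for 48 weeks, so for completers the last doses fall close together. Section 8.1 lets a subject decline one therapy and continue, but the documents do not say how often that happens.
- **Not an endpoint.** Pregnancy is not among the listed safety endpoints.

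Two stronger inferences are tempting. A reader might infer that a subject who stops etanercept early but continues methotrexate has no coverage after the last methotrexate dose. The documents do not support this: the 4 weeks are added to during-study reporting, which on the natural reading reaches the call about 30 to 37 days after the last dose of the investigational products. A reader might also infer that the protocol regards every pregnancy in the 6 months as drug-exposed. It sets a period of avoidance and does not say that. The sentence about semen concerns men whose partner is already pregnant and is not given as the reason for the 6 months.

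**Conclusion.** The inconsistency is real and should be corrected. On the reading most favourable to the plan, about 80% to 84% of the protocol's own 6-month period has no required pregnancy collection; on the 4-week clause alone, about 85%. These figures rest only on taking 6 months as 180 to 184 days and on where during-study reporting ends. They are shares of time; turning them into shares of pregnancies needs an assumption about timing that the documents do not supply.

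The wrong anchor follows from the text itself: the only drug named for the post-treatment window is etanercept, which unrescued methotrexate-monotherapy subjects never receive. Lactation has the same gap against exclusion 217.

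This is a gap in required, active safety collection. On-treatment pregnancies are collected, and the efficacy analysis, alpha and power are unaffected. The point takes no view on how long contraception should last, only that the sections must be reconciled.

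**What to change.** Reconcile Section 9.3 with Section 6.9 for pregnancy and with exclusion 217 for lactation (Section 6.9 sets no breastfeeding period):

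1. Count the reporting period from the last dose of any protocol-required therapy, etanercept or methotrexate, and match it to the period the protocol already states. If the sponsor prefers a shorter window, give the reason and still define it for subjects who receive no etanercept.
2. State that pregnancies and lactation cases learned of later within that period are reportable, as Section 9.2.2 does for serious adverse events.
3. At the existing 30-day call, remind subjects to report any pregnancy, their own or a partner's, in that period, and add this purpose to Section 7.2.7.
4. Check that the Appendix C worksheets can record methotrexate, since their exposure section is laid out for the Amgen product.

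**Cost.** Protocol wording and a line in the call script; no new visit or sample and no change to the analysis. After the call, reporting would be passive, so some pregnancies would still be missed. A few worksheets may arrive after database lock and would be handled in the safety database.

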## 10. STATISTICAL CONSIDERATIONS

### 10.1 Study Endpoints, Analysis Sets, and Covariates

#### 10.1.1 Study Endpoints

##### 10.1.1.1 Primary Endpoint

- ACR 20 response at week 24

##### 10.1.1.2 Key Secondary Endpoint

- MDA response at week 24

##### 10.1.1.3 Other Secondary Endpoints

- Modified NAPSI score and change from baseline at week 24
- Leeds dactylitis score and change from baseline at week 24
- SPARCC enthesitis score and change from baseline at week 24
- ACR 20 response at all other measured timepoints
- MDA response at all other measured timepoints
- Psoriatic Arthritis Disease Activity Score (PASDAS) at all measured timepoints
- ACR 50, ACR 70, and components of ACR at all measured timepoints

- Simplified Disease Activity Index (SDAI) and change from baseline at all measured timepoints
- Clinical Disease Activity Index (CDAI) and change from baseline at all measured timepoints
- Disease activity score (28 joint) using the C-reactive protein formula (DAS28-CRP) and change from baseline at all measured timepoints
- HAQ-DI score and change from baseline at week 24
- SF-36 score and change from baseline at week 24

For subjects with involved BSA  $\geq 3\%$  at baseline:

- sPGA at week 24
- BSA at week 24

#### **10.1.1.4 Safety Endpoints**

- Adverse events
- Serious adverse events
- Laboratory parameters and vital signs

#### **10.1.1.5 Exploratory Endpoints**

- Change from baseline in van der Heijde mTSS at week 24 and week 48
- Non-progression in van der Heijde mTSS defined as change  $\leq 0$  from baseline at week 24 and week 48
- Modified NAPSI score and change from baseline at all other measured timepoints
- Leeds dactylitis score and change from baseline at all other measured timepoints
- SPARCC enthesitis score and change from baseline at all other measured timepoints
- HAQ-DI and change from baseline at all other measured timepoints
- SF-36v2 and change from baseline at all other measured timepoints

For subjects with involved body surface area  $\geq 3\%$  at baseline:

- sPGA at all other measured timepoints
- BSA at all other measured timepoints

### **10.1.2 Analysis Sets**

#### **10.1.2.1 Full Analysis Set**

The full analysis set will include all randomized subjects. Subjects will be analyzed according to their randomized treatment group. Demographics, baseline disease characteristics, and non-psoriasis efficacy analyses will be based on the full analysis set.

